1.2. Metformin Pharmacokinetics

While metformin is generally well-tolerated by patients, the anti-hyperglycemic response between patients is quite variable. With a twice-daily (BID) oral dose of 750 mg, metformin has a plasma elimination half-life of approximately 6 h. Absorption of the tablet occurs predominately in the small intestine, and is mediated through plasma membrane monoamine transporters (PMATs). However, this absorption is often incomplete, resulting in substantial inter-patient variation in drug bioavailability. Mean drug bioavailability is 55% +/- 16%. Because of this, there is large inter-individual variability in metformin pharmacokinetics (11). Steady-state metformin plasma concentrations can range from 54 to 4133 ng/mL (12). While no accumulation in plasma has been seen in patients after multiple doses, metformin elimination is bi-phasic. While initial elimination of metformin from plasma is relatively rapid, there is a second more prolonged elimination phase possibly due to slow uptake and release from a secondary compartment in tissues (11, 13). Metformin exists as a hydrophilic cationic species at physiologic pH, and as such, has severely limited passive diffusion through tissues. Despite this, metformin is still widely distributed throughout the body and is transported to the liver and other peripheral tissues mainly through organic cation transporters 1 and 3 (OCT1/3) (14). Metformin is not metabolized, is poorly plasma protein-bound and is eliminated from the body by renal excretion into the urine (15).

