3.0 ELIGIBILITY CRITERIA AND PARTICIPANT REGISTRATION

Inclusion Criteria:

- 3.1 Patients with confirmed or suspected malignant solid tumor of thoracic origin (e.g., lung, esophageal, thymus, mesothelioma, chest wall, mediastinum, trachea, pleura) with the intent to treat or biopsy by surgery as standard of care. Tumor must be ≥ 1.5 cm.
- 3.2 Patients with multicentric disease are eligible. Samples from all available tumors are requested for research purposes.
- 3.3 Patients with T2DM being treated with metformin (any dose) for a clinical indication at the time of study enrollment are eligible, and will continue metformin treatment as clinically indicated during the presurgical study period. Their dose of metformin will NOT be changed.

Patients not on metformin at the time of study entry must be willing to take metformin extended release (Glucophage® XR, 750 mg QD for 4 days, then 750 mg BID for 3-6 days) for a total of 7-10 days prior to surgery.

Patients do not require a diagnosis of diabetes to be enrolled in the study.

All patients must be willing to keep a drug diary indicating the dates and times of metformin administration.

One patient who has not been treated with metformin will be consented and enrolled. This patient will be asked to provide tumor, adipose, normal lung tissue, and blood samples, and all samples will be collected as described in section 4.2.2. These samples will be taken to serve as a control and are needed in order to optimize the metformin quantification.

- 3.4 Patients must meet the following clinical laboratory criteria:

- Absolute neutrophil count (ANC) $\geq 1,500/\text{mm}^3$ and platelet count $\geq 75,000/\text{mm}^3$.
- Total bilirubin $\leq 1.5 \times$ the upper limit of the normal range (ULN).
- Alanine aminotransferase (ALT) and aspartate aminotransferase (AST) $\leq 3 \times$ ULN.
- eGFR $> 60 \text{ mL/min}/1.73\text{m}^2$ or eCrCL $> 60 \text{ mL/min}$
- [name] Question For lung surgery do we need an INR < 1.6

- 3.5 Ability to give informed consent.

- 3.6 Patients must be willing to provide 20 mL of blood for research use.

- 3.7 Patient must be willing to provide consent for use of archived tissue for research.

Exclusion Criteria:

- 3.8 History of diabetes that is currently being treated without metformin.
- 3.9 Patients with a documented history of alcoholism, or binge drinking disorder.

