3.10 Patients who, at the time of study entry, are not taking metformin for a clinical indication, and who will need a radiographic analysis with an iodinated contrast agent during the metformin study treatment period.

This criterion does not apply to patients taking clinically indicated metformin at the time of study entry.

3.11 History of reactive hypoglycemia.

3.12 History of liver disease as defined with LFTs above those in the inclusion

3.13 Known hypersensitivity to metformin.

3.14 Active or history of lactic acidosis, metabolic acidosis, or diabetic ketoacidosis.

3.15 Patients who are pregnant or breastfeeding.

Participant Registration:

3.16 Following completion of pre-treatment evaluations and informed consent, participants will be registered by a Clinical Research Coordinator via the Norris Cotton Cancer Center's clinical trials management system (Velos or equivalent) . At the time of registration, the following information will be recorded:

[figure not shown]
- Patient's name and subject identification number.
- Patient's date of birth.
- Date of treatment start.

3.13 Eligibility criteria will be verified at the time of registration. A case number will be assigned following registration.

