Diarrhea led to discontinuation of study medication in 0.6% of patients treated with GLUCOPHAGE XR (metformin extended release). Additionally, the following adverse reactions were reported in ≥1.0% to ≤5.0% of GLUCOPHAGE XR patients and were more commonly reported with GLUCOPHAGE XR than placebo: abdominal pain, constipation, distention abdomen, dyspepsia/heartburn, flatulence, dizziness, headache, upper respiratory infection, taste disturbance. Cholestatic, hepatocellular, and mixed hepatocellular liver injury have been reported with post-marketing use of metformin. In rare cases, metformin treatment can result in lactic acidosis; the main risk factors for this serious adverse event are renal impairment, or overdose of drug. While this lactic acidosis toxicity is uncommon, it is recommended that patients not be prescribed metformin if their plasma creatine values are above 1.5 mg/dL (men) or 1.4 mg/dL (women) (35).

Metformin extended release will be stored, dispensed, and accounted for by the DHMC Investigational Pharmacy.

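### The renal entry rule in 3.4 and the creatinine advice in 4.2.3 can disagree for the same patient, and the protocol does not say how to resolve it

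*Combined protocol and SAP*

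**What the plan says.** Section 3.4 is binding: "Patients must meet the following clinical laboratory criteria". Its renal line offers two routes joined by *or*: eGFR above 60 mL/min/1.73 m², or eCrCL above 60 mL/min. Either is enough. The list has no creatinine limit, no estimating equation, no choice of body weight, and no rule for the case where the two estimates fall on opposite sides of 60.

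The exclusions in 3.8 to 3.15 contain no renal criterion. The nearest is 3.14: "Active or history of lactic acidosis, metabolic acidosis, or diabetic ketoacidosis".

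Section 4.2.3, under the toxicities and risks of metformin, discusses lactic acidosis and states that "the main risk factors for this serious adverse event are renal impairment, or overdose of drug". It then reports, citing reference 35, that "it is recommended that patients not be prescribed metformin if their plasma creatine values are above 1.5 mg/dL (men) or 1.4 mg/dL (women". The printed word is *creatine*; the units and context show that creatinine is meant. Nothing in section 3 applies this limit, and nothing in 4.2.3 explains how it relates to the rule in 3.4.

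The patients to whom the study itself supplies the drug are defined in 3.3: "Patients not on metformin at the time of study entry must be willing to take metformin extended release". They need not have diabetes.

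**The concern.** The entry rule and the drug-safety text use different renal measures, and the protocol does not connect them. If a patient can pass 3.4 with a creatinine above the 4.2.3 figure, a site that follows 3.4 literally would give study metformin to someone whom the protocol's own risk section advises against treating. Section 9.3 says participants gain no direct clinical benefit, so the entry rule and the safety text should at least agree.

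There is also a practical problem. With no equation or weight named, two staff members could reach opposite eligibility decisions on the same patient from the same blood result.

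**Working it through.** The plan gives no figure to reproduce here. The check is whether one patient can satisfy 3.4 and also exceed the 4.2.3 limit, and for whom.

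**Inputs from the protocol.** 3.4: eGFR > 60 mL/min/1.73 m² or eCrCL > 60 mL/min. 4.2.3: creatinine above 1.5 mg/dL (men) or 1.4 mg/dL (women).

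**Assumptions, since the protocol names no equation.** Creatinine (Scr) is set just above each limit: 1.51 for men, 1.41 for women.

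- eCrCL, Cockcroft-Gault: (140 − age) × weight / (72 × Scr), × 0.85 for women.
- eGFR, three equations without a race term, with κ = 0.9 for men and 0.7 for women, written for Scr above κ:
  - MDRD: 175 × Scr^−1.154 × age^−0.203, × 0.742 for women.
  - CKD-EPI 2009: 141 × (Scr/κ)^−1.209 × 0.993^age, × 1.018 for women.
  - CKD-EPI 2021: 142 × (Scr/κ)^−1.2 × 0.9938^age, × 1.012 for women.

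**Step 1: eCrCL branch, actual weight.** Setting eCrCL = 60 and solving for weight gives the weight above which the patient is eligible: 60 × 72 × Scr / (140 − age), divided by 0.85 for women.

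| Age | Man, 1.51 mg/dL | Woman, 1.41 mg/dL |
|---|---|---|
| 50 | 6523.2 / 90 = 72.5 kg | 6091.2 / (90 × 0.85) = 79.6 kg |
| 60 | 6523.2 / 80 = 81.5 kg | 6091.2 / (80 × 0.85) = 89.6 kg |
| 65 | 6523.2 / 75 = 87.0 kg | 6091.2 / (75 × 0.85) = 95.5 kg |
| 70 | 6523.2 / 70 = 93.2 kg | 6091.2 / (70 × 0.85) = 102.4 kg |

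Lighter patients fail. A man of 65 years and 80 kg with creatinine 1.6 has 75 × 80 / (72 × 1.6) = 52.1 mL/min.

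**Step 2: eCrCL branch, ideal weight.** Take an ideal weight of about 75 kg for a man of 180 cm and about 57 kg for a woman of 165 cm (assumed heights).

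- Man, 1.51, age 50: 90 × 75 / (72 × 1.51) = 62 mL/min, passes. Age 55: 85 × 75 / 108.72 = 59, fails.
- Woman, 1.41, age 40: 100 × 57 × 0.85 / (72 × 1.41) = 48 mL/min, fails. The estimate falls with age, so she also fails at every later age up to 70.

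**Step 3: eGFR branch.** A man at 1.51 exceeds 60 only up to age 18 (MDRD), 32 (CKD-EPI 2009) or 38 (CKD-EPI 2021). No adult woman at 1.41 exceeds 60 with any of the three. At age 65 the estimates are 46.6 to 50.9 for the man and 37.4 to 41.4 for the woman. In middle-aged and older patients, then, the overlap comes from the eCrCL branch.

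**Step 4: one patient under each convention.** Man, 55 years, 100 kg, 180 cm, creatinine 1.6 mg/dL, above the 4.2.3 limit:

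- eCrCL, actual weight: 85 × 100 / 115.2 = 73.8, eligible.
- eCrCL, adjusted weight (75 + 0.4 × 25 = 85 kg): 85 × 85 / 115.2 = 62.7, eligible.
- eCrCL, ideal weight: 85 × 75 / 115.2 = 55.3, not eligible by this route.
- eGFR, CKD-EPI 2021: 50.6, not eligible by this route.

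He is eligible or not according to a choice that the protocol leaves open.

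**The case against.** The strongest reply is that the protocol contains one entry rule, not two. The 4.2.3 sentence is background with a citation, and it does not tell a site to screen, exclude or stop anyone. That stands. A reader might infer that two eligibility criteria contradict each other; the text does not support this. A reader might also infer that 3.4 is the unsafe rule and the creatinine limit the right one. The documents do not settle that either: they do not say how the cited limit relates to a rule based on eGFR or eCrCL.

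Second, renal risk is not ignored. 3.4 requires at least one estimate above 60, 3.14 excludes past or active acidosis, study-supplied metformin lasts 7 to 10 days, and 9.3 reports no lactic acidosis in 35,619 patient-years. All of this bears on how large the risk is. None of it makes the two passages agree.

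Third, the overlap depends on the weight used. This also stands: with ideal weight it shrinks to a narrow group of men and, at 165 cm, disappears for women aged 40 to 70. But the protocol does not name ideal weight, so the dependence is itself part of the gap.

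Fourth, it is tempting to add a scientific consequence. Section 1.2 says metformin "is eliminated from the body by renal excretion into the urine", and the primary objective is a target for spread, so a loose renal rule might seem to threaten it. No effect on the coefficient of variation has been shown. Sections 1.2 and 4.2.3 attribute variability in exposure to absorption and transport, and 3.3 already admits current users at whatever dose they take. That inference should not be drawn.

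**Conclusion.** The point holds as an unreconciled inconsistency in safety text. One patient can be eligible for study-supplied metformin under 3.4 while 4.2.3 reports advice against prescribing it. With actual weight this needs no extreme patient: a man just above the limit qualifies from about 72.5 kg at 50 or 87 kg at 65, and a woman from about 80 kg or 96 kg. With ideal weight few such patients remain. Both results rest on Cockcroft-Gault, which the protocol does not name.

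The documents give no distribution of age, weight or creatinine, so the number affected among the 20 evaluable patients is unknown; it is probably small. The point deserves a correction but does not undermine the study's design or its primary analysis.

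**What to change.** Reconcile 3.4 and 4.2.3 so that no patient is eligible for study-supplied metformin under one and advised against under the other. In 3.4, name the estimating equation or equations and the body weight to be used, and state which measure governs when eGFR and eCrCL fall on opposite sides of the threshold. In 4.2.3, correct *creatine* to *creatinine* and say how the cited recommendation relates to the entry rule. Which renal rule applies, and which of the two passages changes, is for the sponsor's clinical team to decide.

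The cost is a short wording amendment. No new test is needed, because creatinine already enters both estimates. The laboratory list in 3.4 still carries an open drafting question about INR, so the same amendment can deal with both. Depending on the team's decision, a few otherwise eligible patients might be lost.

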4.3 Study exit

Following surgery, the patient's participation in the study will end. The patient will then be treated as per standard-of-care by her/his treating physician.

4.4 Evaluable patients

Subjects who proceed to a definitive surgical procedure with A) tumor tissue sufficient to provide specimens for research purposes, and B) histologically-confirmed tumor tissue in the surgical specimen will be considered evaluable. Subjects whose surgical specimens do not contain adequate tumor tissue to assess the Primary Endpoint will not be considered evaluable, and will need to be replaced.

4.5 Analyses

1. *Pharmacokinetic analysis of metformin concentrations in plasma, whole blood, and tissues.*

The concentrations of metformin in all samples of blood, plasma, and tissue (tumor, normal, adipose) will be measured by a liquid chromatography (LC) with tandem mass

spectrometry (MS/MS) assay developed in the NCCC Clinical Pharmacology Shared Resource. The average value from the technical triplicates for each biological specimen will be used for calculations. This methodology is established in the NCCC Clinical Pharmacology Shared Resource for measurement of metformin concentrations in mouse tissues/tumors and cultured cells; this methodology will be re-optimized for analysis of human tissues using specimens collected from the single control subject enrolled in this study, in which specimens will be spiked with metformin to generate standard curves

In brief, the current assay consists of plasma protein precipitation using acetonitrile, and filtration over Phenomenex iPhree cartridges. The eluate is dried under nitrogen, resuspended in water, and injected into the LC-MS/MS. In mouse plasma (without full validation), assay accuracy was 91-98%, precision was <15% CV, and recovery was 89%.

2. *Immunohistochemical analysis of AMPK activity of pre- vs. post-metformin treated tumors.*

The goal of this exploratory endpoint is to determine whether metformin treatment alters phosphoprotein markers of AMPK activity in tissues.

In eligible patients, baseline (diagnostic biopsy specimen) and post-metformin (surgical specimen) tumor/normal tissue samples will be sectioned and processed for IHC in the NCCC Pathology Shared Resource. Tissue sections will be immunostained using antibodies against P-ACC(S79), and P-S6(S240/244). P-ACC and P-S6 will be scored using a Histoscore scale (36) that incorporates staining intensity and frequency. We expect metformin treatment to increase P-ACC and decrease P-S6 Histoscores, as metformin treatment should increase AMPK activity.

5.0 DATA COLLECTION, HANDLING AND RECORD KEEPING

5.1 Confidentiality

Information about study subjects will be kept confidential and managed according to the requirements of the Health Insurance Portability and Accountability Act of 1996 (HIPAA). Participants will sign an authorization that includes the following:

- What protected health information (PHI) will be collected from subjects in this study
- Who will have access to that information and why
- Who will use or disclose that information
- The rights of a research subject to revoke their authorization for use of their PHI.

In the event that a subject revokes authorization to collect or use PHI, the investigator, by regulation, retains the ability to use all information collected prior to the revocation of subject authorization.

Loss of patient confidentiality is a risk of participation. Study participant identities will be kept confidential except as required by law. Subjects' samples will be identified by code only (i.e. linked, but de-identified). Patient samples will be de-identified at the time and site of collection. Electronic case report forms, participant, and study information will be kept in the Velos eResearch password protected database (or equivalent). Additionally, documents containing

participant identifiers, such as those from the medical record to confirm eligibility, will be filed in binders and kept in a locked, secure location at the Norris Cotton Cancer Center.

5.2 Data retention

Following closure of the study, the investigator will maintain all site study records in a safe and secure location. The records are maintained to allow easy and timely retrieval, when needed (e.g., audit or inspection) and, whenever feasible, to allow any subsequent review of data in conjunction with assessment of the facility, supporting systems, and staff. Upon completion of study analysis, research information is stored in Dartmouth College Records Management off-site storage located at [name]. Documents are shredded on site after 50 years of storage.

Electronic case report forms, participant, and study information will be kept in the Velos eResearch password protected database (or equivalent) indefinitely.

6.0 STUDY MONITORING, AUDITING, AND INSPECTING

6.1 Safety and Data Monitoring

This study will be monitored by the Data Safety Monitoring and Accrual Committee (DSMAC) of the Norris Cotton Cancer Center. The Committee meets quarterly to review accrual rates and information of all studies that have accrued participants. The DSMAC has the authority to suspend or terminate all research activities that fall within its jurisdiction. In the event that a study is suspended or terminated by the DSMAC, that information will be forwarded to the CPHS office.

6.2 On-Site Monitoring

Clinical research monitoring will be conducted by appropriately trained staff of Dartmouth-Hitchcock Medical Center Clinical Trials Office. This monitoring will include periodic assessment of the regulatory compliance, data quality, and study integrity. Study records will be reviewed and directly compared to source documents and the conduct of the study will be discussed with the investigator. Monitors may request access to all regulatory documents, source documents, CRFs, and other study documentation for on-site inspection. Direct access to these documents is guaranteed by the investigator, who must provide support at all times for these activities.

6.3 Auditing and Inspecting

Participation as an investigator in this study implies acceptance of potential inspection by government regulatory authorities and applicable Dartmouth compliance and quality assurance offices. The investigator will permit study-related audits and inspections by the Dartmouth CPHS, government regulatory bodies, and Dartmouth compliance and quality assurance groups of all study related documents (e.g. source documents, regulatory documents, data collection instruments, study data, etc.) The investigator will ensure the capability for inspections of applicable study-related facilities (e.g. pharmacy, diagnostic laboratory, etc.)

7.0 ADVERSE EVENT REPORTING

Patients will be instructed to report the occurrence of any adverse event. An adverse event is any undesirable event occurring with the use of this procedure. Adverse events will be graded according to the NCI Common Toxicity Criteria Version 4.0. A copy of the CTC version 4.0 can

be downloaded from the CTEP home page (<http://ctep.info.nih.gov>). All appropriate treatment areas should have access to a copy of the CTC version 4.0.

This trial will be independently monitored by the Norris Cotton Cancer Center Data Safety and Accrual Monitoring Committee.

The following definitions will be used to assess causality:

No: The clinical adverse event is definitely unrelated to the study medications (e.g., does not follow a reasonable temporal sequence from study medication administration, present prior to receiving study medication, etc.)

Unlikely: The study medications do not have any reasonable association with the observed experience; however, relationship cannot be definitely excluded.

Possibly: The connection with study medication administration appears feasible, but cannot be excluded with certainty (e.g., follows a reasonable temporal sequence from medication administration, but may also be related to other known factors).

Probably: The clinical experience appears related to the study medications with a high degree of certainty (e.g., follows a reasonable temporal sequence from medication administration and abates upon discontinuation of the medication, cannot be reasonably explained by known characteristics of the patient's clinical state or other modes of therapy administered to the patient, etc.)

8.0 STATISTICAL CONSIDERATIONS

8.1 PRIMARY ENDPOINT – Concentrations of metformin in tumor tissue.

8.2 SECONDARY ENDPOINT – Concentrations of metformin in adipose tissue, tumor-adjacent normal tissue, plasma, and whole blood.

8.3 EXPLORATORY ENDPOINT – Changes in AMPK activity induced by metformin, as determined by changes in P-ACC and P-S6 histoscores between pre- and post-metformin tissue specimens.

8.4 PRIMARY ANALYSIS PLAN – The primary analysis will measure the concentrations of metformin in biological triplicate samples of plasma, whole blood, and tissue specimens from each patient. Metformin concentrations will then be statistically analyzed to determine A) variability between biological triplicates, B) inter-individual variability between patients (within each tissue type; calculate descriptive statistics), and C) relationships between tissue types within each patient (compared by paired *t*-test or two-way ANOVA).

8.5 EXPLORATORY ANALYSIS PLAN – An exploratory analysis will determine whether metformin treatment significantly alters AMPK signaling in tumors compared to baseline. Histoscores from paired (pre- and post-metformin) tissue specimens will be compared by Wilcoxon rank sum test, and the correlation with metformin concentration will be established (the log transformation may be used to comply with the normal distribution assumption). Furthermore, an exploration of the metformin concentrations in plasma blood and tumor tissue and changes in tumor Histoscores will be undertaken using the direct PK-PD model (e.g., sigmoid Emax).

8.6 STATISTICAL TESTING - All statistical tests will be two-sided, and the overall type I error will be 0.05.

8.7 SAMPLE SIZE – We propose to evaluate 20 patients for the Primary Endpoint to account for the wide range (>75-fold) of steady-state plasma concentrations of metformin previously shown in

humans (12). There are no data on intra-tumor concentrations of metformin. As a surrogate, we will use plasma concentrations of metformin under the assumption that plasma and tumors will exhibit similar ranges of variability between patients. We will enroll one additional subject to acquire control tissues, bringing the total study accrual goal to 21 subjects.

The log chi-square test is used to find the minimum detectable coefficient of variation [CV=relative standard deviation (SD)] for metformin in tumor tissues with $n=20$ sample size (number of tumors and patients). To compute the power of the test, we use the fact that the CV is approximately equal to SD on the log scale. Our one-sided power analysis implies that with $n=20$, under the null hypothesis that $CV=SD/\text{mean}=25\%$, the minimum detectable $CV=15\%$ with 90% power and the Type I error alpha=5%.

Based on the high number of patients undergoing surgical resection of lung tumors at DHMC, we project that this study will complete accrual within 24 months.

